# 6.5. Treatment Assessments (Post Week 48 until the End of Blinded Treatment Visit)

#### 6.5.1. Post Week 48 Assessments

After Week 48, all subjects will continue to take their blinded study drugs and attend visits every 12 weeks until the End of Blinded Treatment Visit. Once the last subject completes the Week 48 visit, and Gilead completes the Week 48 analysis, all subjects will return to the clinic (preferably within 30 days) for the End of Blinded Treatment Visit. Study visits are to be completed within ± 6 days of the protocol specified visit date, unless otherwise specified.

- Review of AEs and changes in concomitant medications
- Complete physical examination (Every 48 weeks) (urogenital/anorectal exams will be performed at the discretion of the Investigator) or symptom-directed physical examination as needed
- Vital signs measurement (blood pressure, pulse, respiration rate, and temperature), including weight
- Obtain blood and urine samples as described in Sections 6.10.1 and 6.10.2
- Document study drug dispensation and accountability for all study drugs dispensed
- Subjects who meet the criteria for virologic failure will be managed according to the Management of Virologic Rebound Section 6.11.1 and 6.11.2

#### 6.5.2. End of Blinded Treatment Visit Assessments

Once the last subject completes the Week 48 visit, and Gilead completes the Week 48 analysis, all subjects will return to the clinic (preferably within 30 days) for an End of Blinded Treatment Visit. At the End of Blinded Treatment Visit, if safety and efficacy of B/F/TAF FDC is demonstrated, following review of unblinded data, subjects in a country where B/F/TAF FDC is not available, will be given the option to receive B/F/TAF FDC in an OL extension phase for up to 96 weeks, or until the product becomes accessible to subjects through an access program, or until Gilead elects to discontinue the study in that country, whichever occurs first.

Subjects who receive the OL B/F/TAF FDC will return for study visits every 12 weeks.

Subjects who choose to not receive the OL B/F/TAF FDC will be required to return to the clinic for a 30-Day Follow-up visit following the End of Blinded Treatment Visit. Subjects who have discontinued study drug prior to the End of Blinded Treatment Visit will not be eligible for the OL extension. However, these subjects will be asked to continue attending the scheduled study visits through to the End of Blinded Treatment Visit, and then discontinue from the study after the End of Blinded Treatment Visit.

Treatment assignments will be provided to the investigators within 30 days of the last subject completing the End of Blinded Treatment Visit.

The following will be performed at the End of Blinded Treatment Visit:

- Review of AEs and changes in concomitant medications
- Complete physical examination (urogenital/anorectal exams will be performed at the discretion of the Investigator)
- Vital signs measurement (blood pressure, pulse, respiration rate, and temperature), including weight
- Obtain blood and urine samples as described in Sections 6.10.1 and 6.10.2
- Document study drug dispensation, if applicable, and accountability for all blinded study drugs dispensed
- Subjects who wish to continue in the OL Extension study will receive OL B/F/TAF

#### 6.5.3. OL Extension Assessments

For purposes of study visit identification during the OL extension, study visits will be identified by the number of weeks that have elapsed between the End of Blinded Treatment Visit and the corresponding OL study visit, and labeled with "OL" (eg, Week 12 OL, Week 24 OL, etc.).

All subjects participating in the OL extension phase, without regard to their blinded treatment regimen, will return for study visits at Week 12 OL, and every 12 weeks thereafter for up to 96 weeks.

Study visits are to be completed within  $\pm$  6 days of the protocol specified visit date (based on the End of Blinded Treatment Visit date) unless otherwise specified.

The following will be performed at the OL Extension Visits:

- Review of AEs and changes in concomitant medications
- Complete physical examination (Weeks 48 and 96 OL) (urogenital/anorectal exams will be performed at the discretion of the Investigator) or symptom-directed physical examination, as needed
- Vital signs measurement (blood pressure, pulse, respiration rate, and temperature), including weight
- Obtain blood and urine samples as described in Sections 6.10.1 and 6.10.2

- Document study drug dispensation and accountability for all study drugs dispensed
- Subjects who meet the criteria for virologic failure will be managed according to the Management of Virologic Rebound Section 6.11.1 and 6.11.2

#### 6.6. Post-treatment Assessments

## **6.6.1.** Early Study Drug Discontinuation Assessments

If the subject discontinues study drug prior to the End of Blinded Treatment Visit, the subject will be asked to return to the clinic within 72 hours of stopping study drug for the Early Study Drug Discontinuation Visit. Prior to the End of Blinded Treatment Visit, if a subject discontinues study dosing (for example, as a result of an AE), every attempt should be made to keep the subject in the study and continue to perform the required study-related follow-up and procedures through to the End of Blinded Treatment Visit (see Section 6.7, Criteria for Discontinuation of Study Treatment). If this is not possible or acceptable to the subject or investigator, the subject may be withdrawn from the study.

If the subject discontinues study drug during the OL extension, the subject will be asked to return to the clinic within 72 hours of stopping the study drug for the Early Study Drug Discontinuation Visit, and will be discontinued from both study drug and study.

At the Early Study Drug Discontinuation Visit, any evaluations showing abnormal results indicating that there is a possible or probable causal relationship with the study drug, will be repeated weekly (or as often as deemed prudent by the Investigator) until the abnormality is resolved, returns to baseline (Day 1) value, or is otherwise explained.

The following evaluations are to be completed at the Early Study Drug Discontinuation Visit:

- Review of AEs and changes in concomitant medications
- Complete physical examination (urogenital/anorectal exams will be performed at the discretion of the Investigator)
- Vital signs measurement (blood pressure, pulse, respiration rate, and temperature), including weight
- Obtain blood and urine samples as described in Sections 6.10.1 and 6.10.2
- Document study drug accountability for all study drugs dispensed

# 6.6.2. 30-Day Follow-Up Visit

Subjects who prematurely discontinue study drug during the blinded phase, and refuse to continue in the study through the End of Blinded Treatment Visit will be asked to return to the clinic 30 days after the completion of the Early Study Drug Discontinuation Visit, for the 30-Day Follow-Up Visit.

Subjects who complete the study drug through the End of Blinded Treatment Visit, and who do not wish to participate in the open-label extension, will be required to return to the clinic 30 days after the last dose of study drug, for the 30-Day Follow-Up Visit.

Those subjects who prematurely discontinue study drug during the blinded phase and continue in the study through at least one subsequent visit after the Early Study Drug Discontinuation Visit will not be required to complete the 30-Day Follow-Up Visit.

Subjects who prematurely discontinue study drug during the OL extension will be asked to return to the clinic 30 days after the completion of the Early Study Drug Discontinuation Visit, for the 30-day Follow-Up Visit. The subject will not continue attending the scheduled OL study visits.

Subjects who complete the OL extension phase will be asked to return to the clinic 30 days after the completion of study drug for the 30-day Follow-Up Visit.

For the purpose of scheduling a 30-Day Follow-Up Visit,  $a \pm 6$  days window may be used. The following evaluations are to be completed at the 30-Day Follow-Up Visit:

- Review of AEs and changes in concomitant medications
- Symptom-directed physical examination
- Vital signs measurement (blood pressure, pulse, respiration rate, and temperature), including weight
- Obtain blood and urine samples as described in Sections 6.10.1 and 6.10.2

At the 30-Day Follow-Up Visit, any evaluations showing abnormal results believed to be a reasonable possibility of a causal relationship with the study drugs will be repeated weekly (or as often as deemed prudent by the Investigator) until the abnormality is resolved, returns to baseline (Day 1) value, or is otherwise explained.

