# 6.4. Treatment Assessments (Week 4 - 48)

The following evaluations are to be completed at Weeks 4, 8, 12, 24, 36, and 48 unless otherwise specified.

Study visits are to be completed within  $\pm$  2 days of the protocol specified visit date (based on the Day 1 visit) through Week 12, and completed within  $\pm$  6 days of the protocol specified visit date through Week 36, unless otherwise specified. The visit window at Week 48 will be  $\pm$  6 weeks of the protocol specified visit date, and this clinical visit window coincides with the Week 48 statistical analysis window for HIV-1 RNA.

Regularly scheduled evaluations will be made on all subjects whether or not they continue to receive study drug.

- SF-36, HIV Symptoms Distress Module, WPAI and PSQI to be completed by the subject at Weeks 4, 12 and 48. Subject is to read questionnaire by himself/herself and write/mark answers directly onto questionnaires
- Review of AEs and changes in concomitant medications
- Complete physical examination (Weeks 24 and 48) (urogenital/anorectal exams will be performed at the discretion of the Investigator) or symptom-directed physical examination, as needed
- Vital signs measurement (blood pressure, pulse, respiration rate, and temperature), including weight
- Obtain blood and urine samples as described in Sections 6.10.1 and 6.10.2
- Document study drug dispensation and accountability for all study drugs dispensed.
- Subjects who meet the criteria for virologic failure will be managed according to the Management of Virologic Rebound Section 6.11.1 and 6.11.2

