- f. Study visits are to be completed within ± 6 days of the protocol specified visit date based on the End of Blinded Treatment Visit date, unless otherwise specified.
- g. **Before the OL extension period**, 30-Day Follow-up is required for subjects not enrolling in the OL extension, or those who prematurely discontinue study drugs and do not continue in the study through at least one subsequent visit after the Early Study Drugs Discontinuation Visit.
  - During the OL extension period, subjects who complete the OL extension, or who permanently discontinue study drugs during the OL extension, will be required to return to the clinic 30 days after the last dose of study drugs, for the 30-Day Follow-Up Visit. For the purpose of scheduling a 30-Day Follow-Up Visit,  $a \pm 6$  days window may be used.
- h. **Before the OL extension period**, Early Study Drugs Discontinuation visit is to occur within 72 hours of last dose of study drug. Subjects will be asked to continue attending the scheduled study visits through the End of Blinded Treatment Visit, even if the subject discontinues study drugs.
  - **During the OL extension period,** subjects who discontinue study drug will be asked to return to the clinic within 72 hours of stopping study drugs, for the Early Study Drugs Discontinuation Visit, followed by a 30-Day Follow-Up Visit. The subject will not continue attending the scheduled OL study visits.
- SF-36, HIV Symptoms Distress Module, WPAI, PSQI, to be completed by the subject. Subject is to read questionnaire by himself/herself and write/mark answers directly onto questionnaires.
- j. Any AE or test showing abnormal results that is believed to have a possible or probable causal relationship with the study drug will be repeated weekly (or as often as deemed prudent by the Investigator) until the abnormality is resolved, returns to baseline (Day 1) value, or is otherwise explained.
- k. Symptom-directed physical examination, as needed.
- 1. Post Week 48, complete physical examination and HCV Serology, are to be performed every 48 weeks
- m. Blood pressure, pulse, respiration rate, and temperature.
- n. Females of childbearing potential only. After the Screening visit, positive urine pregnancy tests will be confirmed with a serum pregnancy test.

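### Minor: one visit soon after stopping study drug waives the 30-Day Follow-Up, with no minimum time since the last dose

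*Protocol*

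**What the plan says.** Protocol 6.6.2 deals with blinded-phase subjects who stop study drug early in two paragraphs. Paragraph 1 applies to those who "refuse to continue in the study through the End of Blinded Treatment Visit will be asked to return to the clinic 30 days after". Counting starts when the Early Study Drug Discontinuation (ESDD) Visit is completed. Under paragraph 3, those who stay "through at least one subsequent visit after the Early Study Drug Discontinuation Visit will not be required to complete the 30-Day Follow-Up Visit".

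Appendix 2 footnote g requires the visit of early discontinuers who "do not continue in the study through at least one subsequent visit after the Early Study Drugs Discontinuation Visit". SAP Appendix 1 repeats that footnote. No text says how long after the last dose the qualifying visit must be, or that it must be a scheduled one.

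The surrounding rules are:

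- The ESDD Visit is within 72 hours of stopping (6.6.1), and the 30-Day Follow-Up has a window of 6 days either side (6.6.2).
- Scheduled visits continue off drug and keep their Day 1 timing. Section 6.4 sets windows either side "of the protocol specified visit date (based on the Day 1 visit) through Week 12", and wider ones later.
- All AEs are collected to 30 days after the last dose (7.3.1). Treatment-emergent AEs and laboratory abnormalities are summarized over the same period (8.6.2, 8.6.3; SAP 7.1.5.1, 7.2.2.1).
- For subjects who stop dosing, 6.6.1 says that "every attempt should be made to keep the subject in the study".

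**The concern.** The 30-Day Follow-Up places an AE review and laboratory draw near the end of the period over which safety is assessed. A visit a few days after the last dose cannot do that job, yet as written it discharges the requirement. If the subject then leaves, new non-serious AEs and new laboratory changes between that visit and day 30 have no scheduled point of detection.

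At stake is completeness of safety data in a small group. That group includes people who stopped for toxicity (6.7), and safety and tolerability is the secondary objective.

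**Working it through.** The plan gives no figure to reproduce. The check is how early the qualifying visit can fall.

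**Inputs.** Nominal visit days 28, 56, 84, 168, 252 and 336 (SAP Table 2). ESDD 1 to 3 days after the last dose, within the 72 hours allowed. Window of 6 days, so the earliest day for a follow-up timed from the last dose is 30 − 6 = 24.

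**Example.** Last dose Day 50, ESDD Day 51.

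- Week 8: 56 − 50 = 6 days after the last dose. The waiver applies.
- Safety period ends on Day 50 + 30 = Day 80, so 80 − 56 = 24 days have no scheduled contact if the subject leaves.
- Week 12, if attended: 84 − 50 = 34 days after the last dose.

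**How often the next visit is early.** For each last-dose day L from 1 to 335, take the first nominal visit after ESDD; gap = visit day − L.

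| Stop days | Gap | ESDD at L+1 | ESDD at L+3 |
|---|---|---|---|
| 1–335 (335 days) | under 24 days | 132 (39%) | 120 (36%) |
| 1–335 (335 days) | under 30 days | 166 (50%) | 154 (46%) |
| 1–83, before Week 12 (83 days) | under 24 days | 66 (80%) | 60 (72%) |
| 84–335 (252 days) | under 24 days | 66 (26%) | 60 (24%) |

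The first row can be checked by hand. With ESDD at L+1 the qualifying gaps are 2 to 23, which is 22 days before each of 6 visits: 22 × 6 = 132. With ESDD at L+3 they are 4 to 23: 20 × 6 = 120.

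**Worst case.** With ESDD at L+1 the shortest gap is 2 days, leaving 30 − 2 = 28 days without scheduled review. With a 24-day minimum, the most that can be left is 30 − 24 = 6 days.

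These are shares of possible stop days, not of subjects. They treat stop days as evenly spread and ignore the visit windows of scheduled visits.

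**The case against.** The strongest reply is that little is left after the existing safeguards. AEs must be collected to 30 days after the last dose whatever visits occur (7.3.1), and SAEs and deaths in that period must be reported (7.3.2). AEs and abnormal results thought possibly or probably drug-related are repeated weekly (6.6.1; Appendix 2 footnote j). Discontinuers are asked to keep attending. All of this stands, and it keeps the point minor. It does not close the gap. A reporting duty does not create a contact or a blood draw, and weekly repeats cover only what has already been seen.

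A reader might infer that paragraphs 1 and 3 contradict each other for someone who attends one visit and then leaves. The documents do not firmly support that. The natural reading separates leaving at ESDD from staying on, and the discontinuer limb of footnote g applies that split in favour of the waiver. Asking a subject back is also compatible with not requiring it. Some ambiguity remains: footnote g also requires the visit of subjects not entering the open-label extension, and 6.5.2 bars discontinuers from that extension. Read broadly, that limb would narrow the gap.

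The percentages can also be misread. They show how soon the next visit falls, not how many subjects leave after it. They depend on stopping the count at Week 48, although blinded treatment continues with 12-weekly visits. Extending the same method to Week 96, as an assumption, gives 200 to 220 of 671 stop days under 24 days (30% to 33%).

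**Conclusion.** The point holds as a minor weakness of design. Followed as written, the rule lets a visit 6 days after the last dose, or fewer, replace a contact meant for about day 30. An early next visit is common on the schedule: 36% to 39% of stop days to Week 48, and 72% to 80% before Week 12, under the assumptions above. How many subjects then leave is not given in the documents and is probably small.

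It would be wrong to conclude that follow-up is absent or that AE collection ends at the early visit; 7.3.1 and 7.3.2 say otherwise. The primary endpoint is not affected, because the snapshot uses on-treatment HIV-1 RNA up to 1 day after the last dose (8.5.1.1). Open-label discontinuers are not covered by the waiver.

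**What to change.** 1. In 6.6.2 paragraph 3, Appendix 2 footnote g and the SAP copy, waive the 30-Day Follow-Up only if a visit after ESDD is attended about 30 days or more after the last dose, with the existing 6-day window allowed (day 24 at the earliest).
2. State that a blinded-phase discontinuer who leaves before such a visit is asked back under paragraph 1.

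A subject who stays needs no extra visit. In the example, Week 12 at day 34 meets the rule. The gain there is AE review only, because laboratory results on day 34 fall outside the summary period.

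It may be tempting also to move the paragraph 1 visit to days 24 to 30, so that its laboratory results always fall inside the period. That is not advised. Paragraph 1 times the visit "30 days after the completion of the Early Study Drug Discontinuation Visit, for the 30-Day Follow-Up Visit", which is day 31 to 33 after the last dose when ESDD is 1 to 3 days after it, so the AE review covers the full 30 days. A day-24 visit would leave days 25 to 30 unreviewed.

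An optional tidy-up concerns the anchor for open-label discontinuers. Section 6.6.2 paragraph 4 counts from completion of ESDD, while footnote g says that they "will be required to return to the clinic 30 days after the last dose of study drugs, for the 30-Day Follow-Up Visit". The two should agree.

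The cost is one clause in each of three places, one clarifying sentence, and a few extra visits of an existing type for early leavers who agree to return.

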## 6.7. Criteria for Discontinuation of Study Treatment

Study medication will be discontinued in the following instances:

• Unacceptable toxicity, or toxicity that, in the judgment of the investigator, compromises the ability to continue study-specific procedures or is considered to not be in the subject's best interest

- Subject request to discontinue for any reason
- Pregnancy during the study; refer to Appendix 6
   Note: Female subjects who become pregnant during the study will be discontinued from the study and their study treatment assignment will be unblinded by the investigator and shared with the subject.
- Development of active tuberculosis infection
- Discontinuation of the study at the request of Gilead, a regulatory agency or an institutional review board or independent ethics committee (IRB/IEC)

Study medication may be discontinued in the following instances:

- Intercurrent illness that would, in the judgment of the investigator, affect assessments of clinical status to a significant degree. Following resolution of intercurrent illness, the subject may resume study dosing at the discretion of the investigator.
- Lack of efficacy
- Subject noncompliance

## 6.8. End of Study

The end of study will be the last patient's last observation (or visit).

## 6.9. Post Study Care

After a subject has completed/terminated their participation in the study, long-term care for the subject will remain the responsibility of their primary treating physician.

#### 6.10. Clinical Laboratory Assessments

Blood and urine samples will be collected throughout the study as outlined below, within Section 6, and in Appendix 2 Study Procedures Table.

## 6.10.1. Blood Samples

- Blood sample collection for the following laboratory analyses:
  - Serum pregnancy test (females of childbearing potential only). If the test is positive, the subject will not be enrolled
  - Chemistry profile: alkaline phosphatase, AST, ALT, total bilirubin, direct and indirect bilirubin, total protein, albumin, CPK, bicarbonate, blood urea nitrogen (BUN), chloride, creatinine, glucose, potassium, sodium, amylase (reflex lipase testing is performed in subjects with total amylase > 1.5 × ULN)
    - Calcium, phosphorus, magnesium (Screening and Day 1)

- Metabolic assessments: Fasting (no food or drinks, except water, at least 8 hours prior to blood collection) glucose and lipid panel (total cholesterol, HDL, direct LDL, and triglycerides) collected at Day 1, Weeks 12, 24, and 48, and every 24 weeks thereafter, End of Blinded Treatment Visit, and every 24 weeks in the OL extension phase
  - If the subject has not fasted prior to the visit, the visit may proceed, but the subject must return within 72 hours in a fasted state to draw blood for the metabolic assessments
- eGFR according to the Cockcroft-Gault formula:

Male: 
$$\frac{(140 - \text{age in years}) \times (\text{wt in kg})}{72 \times (\text{serum creatinine in mg/dL})} = \text{creatinine clearance (CLcr) (mL/min)}$$

$$\frac{(140 - \text{age in years}) \times (\text{wt in kg})}{72 \times (\text{serum creatinine in umol/L}) \times 0.6786} = \text{CLcr (mL/sec)}$$
Female: 
$$\frac{(140 - \text{age in years}) \times (\text{wt in kg})}{72 \times (\text{serum creatinine in mg/dL})} \times 0.85 = \text{CLcr (mL/min)}$$

$$\frac{(140 - \text{age in years}) \times (\text{wt in kg})}{72 \times (\text{serum creatinine in umol/L}) \times 0.6786}$$

- Hematology profile: complete blood count (CBC) with differential and platelet count
- CD4+ cell count and percentage
- Plasma HIV-1 RNA
- HBV blood panel (Screening, Week 48, every 48 weeks through End of Blinded Treatment Visit, and Weeks 48OL, 96OL): Hepatitis B virus surface antigen (HBsAg), Hepatitis B virus surface antibody (HBsAb) and Hepatitis B virus core antibody (HBsAb)

The following tests will be conducted by the central laboratory if the following criteria are met:

- If positive HBsAg: reflex testing for plasma HBV DNA, Hepatitis B virus e-antigen (HBeAg) (if negative, reflex Hepatitis B virus e-Antibody [HBeAb]), and quantitative HBsAg
- If positive HBcAb with negative HBsAg and negative HBsAb: reflex testing for plasma HBV DNA (if positive, reflex HBeAg). If HBeAg is performed and found to be negative, reflex HBeAb
- Plasma HBV DNA for patients who are HBV co-infected

HCV antibody (Ab) serology. Subjects who are HCVAb positive will have a HCV RNA test performed (Screening, Week 48, every 48 weeks through End of Blinded Treatment Visit, and Weeks 48OL, 96OL)

